11.3. CLINICAL LABORATORY EVALUATIONS.....	24
11.3.1. Haematology	24
11.3.2. Clinical Chemistry	24
11.3.3. Urinalysis	24
11.4. VITAL SIGN MEASUREMENTS.....	24
11.5. PHYSICAL EXAMINATION	25
11.6. NEUROLOGICAL EXAMINATION.....	25
12. CHANGES IN THE PLANNED ANALYSIS	25
13. REFERENCES.....	25
14. APPENDICES	27
14.1. SCHEDULE OF ACTIVITIES (SoA)	27
14.2. HADS SCORES AND MDS-UPDRS SCORES	30

List of Abbreviations

AE	Adverse Event
ALT	Alanine Transaminase
ANCOVA	Analysis of Covariance
AST	Aspartate Aminotransferase
ATC	Anatomical Therapeutic Chemical
BUN	Blood Urea Nitrogen
CGI	Clinical Global Impression
CGI-C	Clinical Global Impression of Change
CGI-S	Clinical Global Impression of Severity
CMH	Cochran-Mantel-Haenszel
eCRF	Electronic Case Report Form
EoT	End of Treatment
EMA	European Medicines Agency
FAS	Full Analysis Set
FDA	Food and Drug Administration
GGT	Gamma Glutamyl transpeptidase
HADS	Hospital Anxiety and Depression Scale
ICF	Informed Consent Form
IPD	Idiopathic Parkinson's Disease
IWRS	Interactive Web Response System
L-Dopa	Levodopa
LLT	Lower Level Term
LOCF	Last Observation Carried Forward
MAO-B	Monoamine Oxidase-B
MAR	Missing at Random
MDS-UPDRS	Movement Disorder Society - Unified Parkinson's Disease Rating Scale
MedDRA	Medical Dictionary for Regulatory Activities
mg	Milligrams
MMRM	Mixed Model Repeated Measures
MMSE	Mini-mental State Examination
NRS	Numerical Rating Scale
od	Once Daily
PD	Parkinson's Disease
PGI	Patient Global Impression
PGI-C	Patient Global Impression of Change
PP	Per Protocol
PRN	Pro Re Nata (When Necessary)
PT	Preferred Term
RBC	Red Blood Cell
REML	Restricted Maximum Likelihood
SAE	Serious Adverse Event
SE	Standard Error
SGOT	Serum Glutamic-Oxaloacetic Transaminase
SGPT	Serum Glutamic-Pyruvic Transaminase

SoA	Schedule of Activities
SOC	System Organ Class
SOP	Standard Operating Procedures
TEAE	Treatment-Emergent Adverse Events
WHODDE	World Health Organization Drug Dictionary Enhanced
WBC	White Blood Cell

1. Introduction

Safinamide is an alpha-aminoamide derivative, structurally unrelated to any other drug for the treatment of Parkinson's Disease (PD).

Safinamide has both dopaminergic and non-dopaminergic activities. It is a potent, selective and reversible Monoamine oxidase-B (MAO-B) inhibitor, a mechanism associated with enhancement of dopaminergic transmission in the brain. Safinamide is also a state-dependent inhibitor of voltage-gated sodium channels and, at higher concentrations, inhibits calcium channels. These molecular mechanisms act in animal models of PD to increase brain dopamine, extend levodopa (L-Dopa) induced ON-time (dopaminergic actions) and reduce the severity of L-Dopa induced dyskinesia (non-dopaminergic action).

It is suggested that dopaminergic effects through selective and reversible inhibition of MAO-B, and non-dopaminergic effects through state dependent inhibition of voltage-gated sodium channels, are likely to be the principal relevant mechanisms for therapeutic activity in PD.

Safinamide (50mg and 100mg) has been approved by the European Medicines Agency (EMA) and Food and Drug Administration (FDA) for the treatment of mid- to late-stage fluctuating PD subjects as add-on therapy to L-Dopa (alone or in combination with other anti-Parkinson drugs).

Pain is a frequent non-motor symptom of PD, often underestimated and inadequately treated, with a significant impact on patients' quality of life.

There is growing evidence that motor complications and pain may share common pathophysiologic mechanisms that include not only dopaminergic but also non-dopaminergic systems dysfunction, such as glutamatergic hyperactivity.

Results from a post-hoc analysis of the pooled data of two Phase III studies (016 and SETTLE) indicate that safinamide 100 mg/day significantly reduced in fluctuating PD patients the individual use of pain treatments by about 24% and improved two out of three items of the Parkinson's Disease Quality of Life Questionnaire (PDQ-39) related to pain ([Cattaneo et al. 2017](#)).

Therefore, drugs that modulate glutamate release, such safinamide, may be a further option for the treatment of PD chronic pain.

This statistical analysis plan (SAP) defines the statistical methods and data presentations to be used by the PPD Biostatistics department in the analysis and presentation of data for Zambon protocol number Z7219M01 entitled 'A randomised, double-blind, placebo-controlled study to evaluate the efficacy and safety of safinamide 100 mg once daily, as add-on therapy, in idiopathic Parkinson's Disease (IPD) subjects with motor fluctuations and PD related chronic pain'.

This SAP has been written in accordance with International Conference on Harmonisation ([ICH E9](#)) and PPD Global Biostatistics and Programming standard operating procedures (SOPs) and using the final study protocol Version 3.0 (27 October 2020), electronic case report form (eCRF) Version 2.0 (10 January 2020).

2. Objectives

The primary objective is to evaluate the efficacy of safinamide 100 mg once daily (od), compared to placebo, as add-on therapy, for PD related chronic pain.

The secondary objectives include the following:

- 1) To assess the percentage of pain responders.
- 2) To assess the Clinical Global Impression.
- 3) To assess the Patient Global Impression.
- 4) To assess the reduction in use of pain drugs.
- 5) To assess the mood.
- 6) To assess motor and non-motor symptoms.
- 7) To evaluate of the safety and tolerability of safinamide 100mg compared to placebo in fluctuating PD patients with PD related pain.

3. Investigational Plan

3.1. Overall Study Design and Plan

This is a Phase IV, international, multicentre, randomised, double-blind, placebo-controlled study in IPD male and female subjects 30 years of age or older, experiencing motor fluctuations and PD related chronic pain while on stable doses of L-Dopa. The duration of the study for each subject is 19 weeks (including the Screening period). Subjects will be randomised to receive either active or placebo in a 2:1 ratio, respectively. A telephone follow-up call will be performed 1 week after the end of treatment.

[figure not shown]
Study consists of two periods, screening (1-2 weeks) and a treatment period (16 weeks), with a follow-up call at 1 week after treatment, so total duration of 19 weeks.

The Screening visit (Visit 1) should occur up to 14 days before Day 1. At baseline (Visit 2, Day 1), eligible subjects will enter the treatment period and will receive study medication 50 mg (from Day 1 to Day 7) and then 100 mg (from Day 8 onwards), to be taken orally once daily (od). Following completion of all baseline assessments, they will receive the first dose of study medication at the study centre. Thereafter, study drug will be taken, at home, each morning along with their first morning dose of L-Dopa and other (if any) PD medications. On Day 8 the dose of study drug will be increased, at home, to 100 mg od. Each subject will receive treatment for 16 weeks, with visits at Week 0/Day 1 (baseline) and at Weeks 4, 8 and 16 (or early termination).

From day 1 onwards, participant will record the use of PRN medications along with indicating the worst pain experienced on a daily basis.

Diagram of Study Schedule:

Figure 1: Diagram of Study Schedule

Randomisation is in a 2:1 ratio of active:placebo; up to 132 participants will be screened to achieve up to 105 randomized, to have approximately 84 patients complete the study (56 in the active and 28 in the placebo group respectively). The detailed description is present in [Section 4.1](#).

Subjects will take their allocated study drug in accordance with the assigned regimen:

Safinamide: 50 mg (from Day 1 to Day 7) and then 100 mg (from Day 8 onwards)
or
Placebo: 50 mg (from Day 1 to Day 7) and then 100 mg (from Day 8 onwards)

3.2. Study Endpoints

The primary endpoint measured in this study will be:

- The change from baseline to Week 16 in pain severity (“average worst pain experienced in the last 7 days”), as assessed by an 11-point Numerical Rating Scale (NRS).

The secondary endpoints measured in this study will be:

- The percentage of pain responders defined as the subjects with reduction in pain severity of ≥ 2 points (“average worst pain experienced in the last 7 days”), at weeks 4, 8 and 16 as assessed by an 11-point NRS, compared to baseline
- The pain severity score (average worst pain score using 11-point NRS Scale) at week 4, 8.

- The Clinical Global Impression of Severity (CGI-S) score at weeks 4, 8 and 16 (rated by Investigator),
- The change from baseline to Weeks 4 8 and 16 in the Clinical Global Impression of Change (CGI-C) score rated by Investigator,
- The change from baseline to Weeks 4, 8 and 16 in the Patient Global Impression of Change (PGI-C) score rated by the subject
- The percentage of subjects with a reduction in number of days using concomitant pain drugs in the 7 days before each visit at Weeks 4 8 and 16.
- The number of days with PRN pain medication in the 7 days before each visit at Week 4, 8 and 16 (by analysing 7-day intervals before each visit).
- The change from baseline to week 16 in the Hospital Anxiety and Depression Scale (HADS) score.
- The change from baseline to weeks 4, 8 and 16 in the Movement Disorder Society - Unified Parkinson's Disease Rating Scale (MDS-UPDRS) (total score and sub scores) during the "ON" phase.

Tolerability will be assessed by means of incidence of treatment emergent adverse events.

Safety variables include physical and neurological examinations, vital signs (blood pressure and heart rate) and clinical safety laboratory values (haematology, clinical chemistry).

4. General Statistical Considerations

Continuous data will be summarised using summary statistics (i.e. n, mean, standard deviation, median, minimum, and maximum). For the summary statistics of all continuous data, minimum and maximum values will be displayed to the same level of precision as reported, unless otherwise specified. Mean and median will be displayed to one level of precision greater than the data collected. Standard deviation will be displayed to two levels of precision greater than the data collected.

Categorical data will be described using the subject count and percentage in each category. When counts are presented, in cases where the count is zero, the percentage will not be displayed in order to draw attention to the non-zero counts. A row denoted 'Missing' will be included in count tabulations where specified on the shells to account for missing values. The denominator for all percentages will be the number of populated subjects in that treatment within the analysis set of interest, unless otherwise specified. Frequency statistics will be displayed using one decimal place except for the display of 100% frequency which will be displayed as 'XX (100)'.

P-values will be rounded to three decimal places. If a p-value is less than 0.001 it will be reported as '<0.001'. If a p-value is greater than 0.999 it will be reported as '>0.999'. Confidence intervals will be displayed to one level of precision greater than the data

collected. Data will be displayed in all listings sorted by treatment group, country, centre, and subject ID.

Unless otherwise specified, baseline will be defined as the last non-missing evaluation prior to or on the date that the first dose of treatment is taken. Study day is defined in relation to the date of first dose of study drug. Therefore, when an assessment date is before the first dose:

Study day = assessment date - first dose date of study drug

and when an assessment is on or after the first dose:

Study day = assessment date - first dose date of study drug + 1

All analyses will be conducted using SAS Version 9.4 or higher and all data will be summarised based on the visit name collected on the eCRF page.

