4.4. End of Study Definition

A participant is considered to have completed the study if he/she has completed all phases of the study including the follow-up phone call after Visit 5 (End of Treatment) which is the last scheduled procedure shown in the Schedule of Activities.

The end of the study is defined as the date of the last visit of the last participant in the study last scheduled procedure shown in the Schedule of Activities for the last participant in the trial globally.

5. Study Population

Prospective approval of protocol deviations to recruitment and enrollment criteria, also known as protocol waivers or exemptions, is not permitted.

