- Administer subject's first dose of study medication (50 mg) at the study centre.
- Instruct participants to take the study medication, once daily, in the morning, along with their usual dose of L-Dopa. During Week 1 subject will take 50 mg, which will be increased up 100 mg at home on Day 8.
- Dispense study medication for the next 28 days.
- Re-issue electronic diary with instructions for the NRS pain assessment to be completed daily over the 7 consecutive days immediately prior to the visit at week 4 (Visit 3) and the intake of PRN pain medication to be recorded daily according to use.
- Recording of prior medications, of concomitant medications and therapies.
- Recording of AEs (Section 8.3).

When scheduling Visits 3, 4 and 5, bear in mind that:

- where possible, the subject should be in an optimal ON state, i.e. at least 1 hour after the morning dose L-Dopa and study medication.
- the questionnaires should be completed at the approximately on the same time of the day as at the baseline visit.

COVID- 19 outbreak: in order to ensure the continuity of the study, limiting the subjects' exposure to infection and overcoming travel restriction imposed by governments, a Contingency

Plan has been finalized describing alternative procedures to be adopted in the study in order to mitigate the restrictions and keeping participants in the trial (see Appendix 10 for details).

Visit 3 & Visit 4: interim visits (Day 28 & Day 56)

- Completion of MDS-UPDRS (part IB and II), and PGI-C by the subject.
- Completion of MDS-UPDRS (part IA, III and IV), CGI-S and CGI-C by the rater.
- Recording of concomitant medications and therapies.
- Recording of AEs.
- Drug accountability.
- Review and evaluate daily diary (provide additional daily diary training, as required).
- Re-issue electronic diary at weeks 4 and 8, with instructions for the NRS pain assessment and the intake of PRN pain medication to be completed daily over the 7 consecutive days immediately prior to the next visit (Visits 4 & 5).
- Dispense study medication for next period.

COVID- 19 outbreak: in order to ensure the continuity of the study, limiting the subjects' exposure to infection and overcoming travel restriction imposed by governments, a Contingency Plan has been finalized describing alternative procedures to be adopted in the study in order to mitigate the restrictions and keeping participants in the trial (see Appendix 10 for details).

Visit 5: End of Treatment (Day 112)

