Following completion of 16 weeks' of treatment or in the event of premature discontinuation, the following End of Treatment (EOT) assessments and procedures should be performed.

- Neurological & Physical examination.
- Vital signs (heart rate, systolic and diastolic blood pressure measured after at least 5 minutes in the supine position).
- MDS-UPDRS (part IB and II), HADS and PGI-C completed by the participant.
- MDS-UPDRS (part IA, III and IV), CGI-S and CGI-C completed by the rater.
- Obtain blood sample for clinical laboratory assessments (haematology and clinical chemistry).
- Obtain urine sample only for WOCBP for urine (dipstick) pregnancy test.
- Record any changes or new concomitant medications and therapies.
- Record any AEs.
- Review and evaluate daily e-diary.
- Drug (all used & unused study medication) and final accountability.
- Collect e-diary.
- Agree on day & time for the follow up call in one weeks' time.

COVID- 19 outbreak: in order to ensure the continuity of the study, limiting the subjects' exposure to infection and overcoming travel restriction imposed by governments, a Contingency Plan has been finalized describing alternative procedures to be adopted in the study in order to mitigate the restriction and keeping participants in the trial (see Appendix 10 for details)

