8.1.1. Pain Assessments

The primary efficacy endpoint for the study is the mean change in pain severity ("average pain experienced in the last 7 days"), as assessed by an 11-point NRS, from baseline to week 16.

Pain severity data will be derived from the daily diary.

Daily Diary

An electronic diary will be completed daily by each participant as follows:

- to record the PD pain score at screening (Visit 1), by completion of an 11-point NRS, to confirm eligibility
- the NRS score is calculated over 7 consecutive days immediately prior to baseline (Visit 2/Day 1) and Visits 3, 4 and 5/EOT/ET (Weeks 4, 8 and 16), completion of an 11-point NRS, to allow for the assessment of the average pain experienced in the last 7 days during which patient records on a daily basis the most severe pain using an 11-point NRS.
- on a daily basis from baseline onwards, an accurate record of the use of PRN pain medication for PD-associated pain (Section 10.1.6.2).

Daily Diary Training

At the screening visit, the Investigator (or other trained, qualified personnel) will reinforce recognition of PD-related chronic pain, as well as the use of the daily diary.

On each visit, the Investigator will instruct the participant to complete the daily diary at home for the 7 consecutive days immediately prior to the next visit.

Participants will record the intensity of their PD-associated pain, as the worst pain experienced over the past 24 hours, (from 0 [no pain] to 10 [worst possible pain]) using an 11-point NRS. Pain intensity should be recorded if possible, in the evening before going to sleep. If the subject suffered from more than 1 PD-associated pain, the more severe pain will be documented.

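### With visits assigned by eCRF visit name and no early-termination rule, early-termination scores can be analysed as Week 16 and escape the SAP's missing-data rules

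*SAP*

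**What the plan says.** **Assignment rule.** SAP 4 (General Statistical Considerations) says that "all data will be summarised based on the visit name collected on the eCRF page". The same section defines study day, but no analysis window uses it.

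**Where ET sits.** Three places put ET with Visit 5/Week 16:
- Protocol 8, Visit 5 (End of Treatment, Day 112): "in the event of premature discontinuation, the following End of Treatment (EOT) assessments and procedures should be performed". The list that follows includes "MDS-UPDRS (part IB and II), HADS and PGI-C completed by the participant", with CGI-S, CGI-C and the other MDS-UPDRS parts completed by the rater.
- Protocol 8.1.1, on the 7-day pain average: "immediately prior to baseline (Visit 2/Day 1) and Visits 3, 4 and 5/EOT/ET (Weeks 4, 8 and 16".
- SAP 3.1: "with visits at Week 0/Day 1 (baseline) and at Weeks 4, 8 and 16 (or early termination".

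No ET visit appears in the visit list of SAP 5 or in either Schedule of Activities, although Protocol 7.2 sends the reader to that schedule for what to collect at discontinuation. The only end-of-treatment eCRF page named in SAP 10 is the questionnaire-status page for V5 EoT Week 16.

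**Missing-data rules.** SAP 10.1 describes the MMRM estimate as if withdrawn patients had continued like their peers. SAP 10.2b fills missing records after discontinuation with the patient's highest pain score since baseline and leaves intermittent gaps alone. SAP 10.3 counts a missing responder value as non-response at each visit.

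**The concern.** All three missing-data provisions assume that a patient who stops early has no Week 16 value. The visit-name rule, combined with ET assessments done under the Visit 5 heading, can supply one. A score taken after a few weeks would then stand as the 16-week result.

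At stake is whether the planned checks do what the SAP says they do for patients who leave early. For the scales collected at the visit itself (HADS, CGI-S, CGI-C, PGI-C, MDS-UPDRS) no diary requirement limits the problem. HADS is the plainest case: its only post-baseline time point is Week 16, so an early score could enter the ANCOVA directly as the outcome.

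**Working it through.** **1. The plan's own figures.** Inputs (SAP 4.1): difference 1 point, SD 1.5, 5% significance, 80% power, 56:28 completers, 105 randomised. Sidedness is not stated there; two-sided is assumed.
- Noncentrality = 1 / (1.5 × √(1/56 + 1/28)) = 1 / (1.5 × 0.2315) = 2.88 on 82 degrees of freedom, giving 81.2% power. At 54:27 power is 79.8%, so 84 is the smallest 2:1 total that reaches 80%.
- 84 / (1 - 0.20) = 105. The stated numbers reproduce.

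**2. Patients exposed.** 105 - 84 = 21, and 21/105 = 20%. With equal dropout this is 70 - 56 = 14 on safinamide and 35 - 28 = 7 on placebo. It is a ceiling, for three reasons:
- Some who leave will not attend an ET visit.
- For pain, SAP 10.1 requires at least 4 of 7 daily scores. The documents differ on whether these would exist. SAP 3.1 has patients "indicating the worst pain experienced on a daily basis" from Day 1, while Protocol 8 (Visit 2) has the "NRS pain assessment to be completed daily over the 7 consecutive days immediately prior to the visit at week 4 (Visit 3". Under the second reading an unplanned ET visit may have no valid average, and 10.2b and 10.3 then work as intended.
- Protocol 4.4 counts as completers only those who "completed all phases of the study including the follow-up phone call after Visit 5 (End of Treatment", so a non-completer may have a genuine Week 16 score.

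If 0%, 25% or 100% of the 21 have an ET score stored as Week 16, that is 0, about 5, or 21 patients.

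**3. What happens to each rule for such a patient.**
- *10.2b.* Imputed value = max(baseline, later scores) ≥ baseline, so the imputed change is ≥ 0. A stored ET score is not missing, so its own change is used, which can be negative.
- *10.2b, Week 8.* If the patient left between Weeks 4 and 8, an ET score labelled Week 16 makes the empty Week 8 look intermittent, and it is left unimputed.
- *10.3.* An ET score at least 2 points below baseline makes the patient a Week 16 responder instead of a non-responder. Each 10% of the 21 meeting that criterion is 21 × 0.10 = 2.1 patients.
- *HADS, CGI, PGI-C, MDS-UPDRS.* The ET value is analysed as Week 16.

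**4. Direction, tested on 10.2b.** Assume mean changes of -2 (safinamide) and -1 (placebo), an imputed change of 0, and ET scores equal to the arm mean for every dropout.

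| Dropout, safinamide / placebo | 10.2b as stated | ET stored as Week 16 |
|---|---|---|
| 20% / 20% | 0.80×2 - 0.80×1 = 0.80 | 2 - 1 = 1.00 |
| 10% / 30% | 0.90×2 - 0.70×1 = 1.10 | 2 - 1 = 1.00 |

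The difference rises in one case and falls in the other.

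**5. Direction, tested on responders.** Assume every dropout has an ET score and the same share, 10% to 50%, meets the criterion in both arms. With 20% dropout in each arm, both gain 2 to 10 percentage points and the difference does not move. With 30% against 10% dropout, it shifts by (0.30 - 0.10) × 10% to 50% = 2 to 10 points, in the direction of the arm with more dropout.

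**The case against.** **The eCRF is unseen.** The protocol passages say which procedures are done at ET, not which analysis visit they receive, and a separate ET visit name would remove the misassignment. This stands. A reader might infer that early scores are in fact being counted as Week 16; the documents show only that nothing in them prevents it.

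**The visit-name sentence concerns summaries, and pain comes from the diary.** True, but if the sentence does not govern the models, the SAP has no visit-assignment rule for them at all. The 7-day average is anchored to a site visit, so that visit's name still decides the slot.

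**The primary result may hardly move.** This largely stands. The MMRM in SAP 10.1 lists treatment, country, visit, pain medication and baseline, with no treatment-by-visit term. As written it estimates one treatment effect across visits, so relabelling a score's visit may change little. If that term were added to obtain a Week 16 difference, the labelling could matter more. A reader might infer a loss of power or a known bias in the primary analysis; the documents support neither.

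**The checks need not become milder.** Also correct. Step 4 of the working shows the difference moving either way. Even for one patient the direction is not fixed: if the worst value excludes the ET score, someone leaving with worsening pain could have an ET score above the imputed one.

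**Conclusion.** The gap is real and should be closed, with medium confidence because it depends on an eCRF that was not available. Followed literally, and without a separate ET visit name, the plan turns an early score into a Week 16 value. The 10.2b and 10.3 rules then do not apply to that patient, and the other scales carry an early value as a 16-week result.

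The exposure is 0 to 21 of 105 patients (20%), with the upper end unlikely for pain. That ceiling rests on the plan's own dropout assumption. The effect on treatment differences is undetermined in sign and size: it depends on how dropout splits between arms and on what the ET scores are, and neither is known. This is therefore an unstated rule that lets the missing-data checks be bypassed, not a demonstrated bias in favour of safinamide.

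**What to change.** Before unblinding, add to SAP 4:

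- (a) Scheduled on-treatment visits, including those delayed under the COVID-19 contingency plan (Protocol Appendix 10), keep their eCRF visit name.
- (b) An ET assessment before Day 109 (the protocol's Day 112 - 3) is not a Week 16 value. Week 16 is missing for that patient, and 10.1, 10.2b and 10.3 apply.
- (c) Such an assessment fills Week 4 or Week 8 only if its study day lies in that visit's protocol window (Day 28 ± 3, i.e. 25-31, or Day 56 ± 3, i.e. 53-59) and the scheduled visit is missing. Otherwise it is kept as a separate ET record, listed, and counted towards the 10.2b worst value.
- (d) The same rule covers HADS, CGI, PGI-C and MDS-UPDRS. An ET HADS before Day 109 is listed but left out of the Week 16 ANCOVA.

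If the eCRF already names ET separately, say so and keep (b) to (d).

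The cost is one SAP paragraph and one derivation. No new data are needed, since SAP 11.1.6 already draws early withdrawals from the study completion/termination page. The downside is a few fewer observed Week 16 values, and some ET scores, notably HADS, that are only listed.
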